10.6. Appendix 6: Derived and Transformed Data

10.6.1. General

Multiple Measurements at One Time Point

 There are no scheduled multiple measurements, however, if multiple measurements are recorded at a given time point the following process will be followed, unless a process for selection of the measurement for the visit is specified: Mean of the measurements will be calculated and used in any derivation of summary statistics but if listed, all data will be presented. Subjects having both High and Low values for Normal Ranges at any post-baseline visits for safety parameters will be counted in both the High and Low categories of "Any visit post-baseline" row of related summary tables.
Study Day

 Calculated as the number of days from date of first dose of mepolizumab: 
 Ref Date = Missing → Study Day = Missing Ref Date < Date of first dose of mepolizumab → Study Day = Ref Date – Date of first dose of mepolizumab Ref Date ≥ Date of first dose of mepolizumab → Study Day = Ref Date – (Date of first dose of mepolizumab) + 1

10.6.2. Study Population

Demographics	
Age	

 Only year of birth was collected for subjects; actual birth data was not collected. GSK standard IDSL algorithms will be used for calculating age where the birth date of all subjects will be imputed as '30th June'. Birth date will be presented in listings as 'YYYY'. Each subject's derived age will be calculated as an integer value based on their imputed date of birth relative to the date of the subject's screening visit (Visit 1). [(30th June of the year of birth reported on eCRF – date of Screening)/365.25] 	
Body Mass Index (BMI)	

 Calculated as Weight (kg) / Height (m)² 	
Percent Predicted FEV1	

 FEV1 % of predicted normal will be derived using the Global Lung Function Initiative 2012 look-up tables which are based on the Quanjer equations [Quanjer, 2012] according to the Race/Ethnicity designations specified below: 	
Collected Race ^[1]	Quanjer Designation
African American/African Heritage	African-American calculation will be applied
American Indian or Alaskan Native	Other calculation will be applied

Demographics																													
Asian-Central/South Asian Heritage	South East Asian calculation will be applied																												
Asian-East Asian Heritage	North East Asian calculation will be applied																												
Asian-Japanese Heritage	Other calculation will be applied																												
Asian- Southeast Heritage	South East Asian calculation will be applied																												
Native Hawaiian or Other Pacific Islander	Other calculation will be applied																												
White-Arabic/North African Heritage	Caucasian calculation will be applied																												
White-White/Caucasian/European Heritage	Caucasian calculation will be applied																												
NOTES:																													
1. If multiple races are selected for a single subject then the "Other" calculation will be applied.																													
FEV₁/FVC Ratio																													

 Pre- and post-bronchodilator FEV₁/FVC ratio will be calculated as the ratio of the FEV₁ and FVC values. 																													
Length of Omalizumab (Xolair) Use																													

 Number of days exposed to Omalizumab (Xolair) will be calculated based on the formula: For subjects receiving Omalizumab (Xolair) monthly: Duration of Exposure in Days = Last Omalizumab dose – (First Omalizumab dose) + 29 For subjects receiving Omalizumab (Xolair) twice monthly: Duration of Exposure in Days = Last Omalizumab dose – (First Omalizumab dose) + 15 																													
Baseline OCS daily dose																													

 Only corticosteroids administered via oral, intravenous (IV) and intramuscular (IM) routes are to be considered when calculating a subject's total daily prednisone/prednisolone asthma maintenance dose at baseline. All steroids administered via a sublingual route will also be considered as oral. The corticosteroid conversion factors shown below will be used, regardless of the route of administration, to scale each corticosteroid dose to a prednisone equivalent dose. These three routes of administration (oral, IV and IM) are to be considered equivalent as it has been noted that the bioavailability of methylprednisolone is considered to be roughly equivalent following administration as an oral, IV or IM steroid. 																													
Standardised Medication Name																													

  
 Standardised Medication Name	
 
 Scaling Factor	
   
 Betamethasone	8.33	
 
 Betamethasone Dipropionate	8.33	
 
 Betamethasone Sodium Phosphate	8.33	
 
 Cortisone	0.2	
 
 Cortisone Acetate	0.2	
 
 Cortivazol	17	
 
 Deflazacort	0.833	
 
 Dexamethasone	6.67	
 
 Dexamethasone Sodium Phosphate	6.67	
 
 Fludrocortisone Acetate	0	
 
 Hydrocortisone	0.25	
 
 Hydrocortisone Sodium Succinate	0.25	
  
		Standardised Medication Name		Scaling Factor		Betamethasone	8.33	Betamethasone Dipropionate	8.33	Betamethasone Sodium Phosphate	8.33	Cortisone	0.2	Cortisone Acetate	0.2	Cortivazol	17	Deflazacort	0.833	Dexamethasone	6.67	Dexamethasone Sodium Phosphate	6.67	Fludrocortisone Acetate	0	Hydrocortisone	0.25	Hydrocortisone Sodium Succinate	0.25
Standardised Medication Name																													
Scaling Factor																													
Betamethasone	8.33																												
Betamethasone Dipropionate	8.33																												
Betamethasone Sodium Phosphate	8.33																												
Cortisone	0.2																												
Cortisone Acetate	0.2																												
Cortivazol	17																												
Deflazacort	0.833																												
Dexamethasone	6.67																												
Dexamethasone Sodium Phosphate	6.67																												
Fludrocortisone Acetate	0																												
Hydrocortisone	0.25																												
Hydrocortisone Sodium Succinate	0.25																												

Demographics	
Hydrocortisone Sodium Phosphate	0.25
Meprednisone	1
Methylprednisolone	1.25
Methylprednisolone Acetate	1.25
Methylprednisolone Sodium Succinate	1.25
Methylprednisone	1.25
Methylprednisone Acetate	1.25
Methylprednisolone Sodium Succinate	1.25
Methylprednisone	1.25
Methylprednisone Acetate	1.25
Prednisolone	1
Prednisolone Acetate	1
Prednisolone Hemisuccinate	1
Prednisolone Sodium Succinate	1
Prednisone	1
Prednisone Acetate	1
Triamcinolone	1.25
Triamcinolone Acetonide	1.25

10.6.3. Efficacy

Patient Reported Outcomes/Questionnaires	
ACQ-5	

 Each question on the ACQ-5 is scored on a 7-point scale from 0 = no impairment to 6 = maximum impairment. The questions are equally weighted and the ACQ-5 score will be the mean of the 5 questions, thus giving a score between 0 (totally controlled) and 6 (severely uncontrolled) [Juniper, 1999; Juniper, 2005]. If a subject does not complete 1 of the 5 questions at a visit, then the ACQ-5 score will be the mean of the responses to the remaining 4 questions at that visit. If a subject does not complete more than 1 of the 5 questions at a visit, then their ACQ-5 score will be set to missing at that visit. A subject will be deemed a responder if the subject has a ≥ 0.5 reduction in ACQ score from Baseline. ACQ-5 Responder/Non-responder category will be missing if the overall ACQ-5 score is missing. 	
St George's Respiratory Questionnaire (SGRQ)	

 The SGRQ comprises 50 questions with a recall period of 4 weeks. Scores are expressed as the percentage of overall impairment with 100 equal to the worst possible health and 0 the best. Scoring of each domain of the SGRQ (Symptoms, Activity, Impacts) and the Total score are described in the St George's Respiratory Questionnaire Manual (Version 2.3). 	

Patient Reported Outcomes/Questionnaires

Treatment Satisfaction with Medication Questionnaire (TSQM-9)

- TSQM Scale scores range from 0 to 100, with higher scores indicating higher satisfaction. No computed score should be lower or higher than these limits. [Atkinson, 2005]
- Effectiveness scale: $([(\text{Item 1} + \text{Item 2} + \text{Item 3}) - 3] \div 18) \times 100$
If one item is missing: $([(\text{Sum of Item 1} + \text{Item 2} + \text{Item 3})] - 2) \div (12) \times 100$
- Convenience scale: $([\text{Sum of Item 4 to Item 6}] - 3) \div 18 \times 100$
If one item is missing: $([\text{Sum of Item 4 to Item 6})] - 2) \div (12) \times 100$
- Overall Satisfaction scale: First recode Item 9 = $(\text{Item 9} - 1) \times 5/6$
- Then: $([\text{Sum of Item 7 to Item 9}] - 3) \div (12) \times 100$
If any one Item is missing: $([\text{Sum of Item 7 to Item 9})] - 2) \div (8) \times 100$

Exacerbations

An exacerbation of asthma as defined as:

Worsening of asthma which requires use of systemic corticosteroids¹ and/or hospitalisation and/or Emergency Department (ED) visits.

- ¹For all subjects, i.v. or oral steroid (e.g., prednisone) for at least 3 days or a single IM CS dose is required. For subjects on maintenance systemic corticosteroids, at least double the existing maintenance dose for at least 3 days is required.
- Within each subject, exacerbations that occurred less than seven days apart will be collapsed into a single exacerbation. Exacerbations for which the collapsing has already been performed will be included in the summaries and analyses. Exacerbations will be displayed in listings as captured within the eCRF. Exacerbations which are collapsed into a single exacerbation will be highlighted.
- The collapsed exacerbation records will be constructed as follows:
 - Start date (ASTDT) is the start date of the first exacerbation in the series
 - End date (AENDT) is the end date of the last exacerbation in the series
 - Outcome (CEOUT) is the worst outcome in the series (worst to best is Fatal, Not Resolved, Resolved)
 - Cause (EBCAUSE) is the cause associated with the first exacerbation in the series
 - Withdrawal due to exacerbation (EBWD), OCS taken for exacerbation (OCSEXB), corticosteroids taken for exacerbation (CTSEXB), hospitalization due to exacerbation (HSPEXB), emergency visit due to exacerbation (EREXB), and intubation for exacerbation (INTUBEXB) are set to 'Y' if any value for the respective variable in the series equals 'Y'
 - Number of telephone calls (TPCNUM), home day visits (HMDYVSN), home night visits (HMNTVSN), home day+night visits (HMDYNTV), office visits (OFCVSN), urgent care/outpatient visits (UCOUTVSN), emergency room visits (ERVSN), days in intensive care (ICSDYNUM), days in general ward (GWDYNUM) and days hospitalized (HSPDYNUM) are the sum of all of the values in the series for each respective variable

Blood Eosinophils

- Blood eosinophils will be log-transformed prior to analysis. Summary statistics will include geometric mean, and a measure of spread (SD or SE) on the natural log scale.

- If a blood eosinophil count of zero is reported, it will be imputed with half of the lowest possible blood eosinophil count, where applicable, prior to log transforming the data (Note: this imputation has typically been $0.5 * 0.01 \text{ GI/L} = 0.005 \text{ GI/L}$ for previous mepolizumab studies).

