#### **7.3.2.1. Questionnaires**

It is requested that questionnaires are administered at the same time of day during each visit (as applicable). They should be presented to the subject in a consistent order at each study visit. To avoid influencing the subject's response, the subjects should not be told the results of diagnostic tests prior to completing the questionnaires and the questionnaires should be completed before any procedures are performed on the subject. All questionnaires will be completed using an electronic device at clinic. Adequate time should be allowed to complete all items on the questionnaires and the questionnaires must be reviewed by the investigator or designated study staff for completeness and, if necessary, the subject must be encouraged to complete any missing items.

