#### **7.3.2.1.4. Treatment Satisfaction Questionnaire for Medication (TSQM-9)**

The Treatment Satisfaction Questionnaire for Medication (TSQM-9) measures satisfaction with medication on 3 domains of effectiveness, convenience and global satisfaction [Atkinson, 2004; Bharmal, 2009]. The TSQM-9 has been demonstrated to be a reliable and valid measure of satisfaction with medication. Each of the 9 items is scored by the subject on a 5 or 7 point scale with the ends representing extreme dissatisfaction to extreme satisfaction. The total score is reported as score of 0 to 100 with higher scores representing higher satisfaction. Questions are framed to ask about current satisfaction with medication ( see [Appendix 12](#)).

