2.2. Study Objectives and Endpoints

The below objectives and endpoints will be assessed when subjects with a severe eosinophilic asthma phenotype who are not optimally controlled on omalizumab are directly switched from omalizumab to mepolizumab:

Objectives	Endpoints
Primary Objectives	Primary Endpoints

 To describe in a pragmatic situation/setting whether there is an improvement in asthma control from the beginning to the end of the study 	
 Mean change from baseline in Asthma Control Questionnaire-5 (ACQ-5) score at Week 32
Secondary Objectives	Secondary Endpoints

 To determine whether there is an improvement in Health related Quality of Life (HR-QoL) To determine the frequency of asthma exacerbations To evaluate the pharmacodynamic effects 	
 Mean change from baseline in St. George's Respiratory Questionnaire (SGRQ) score at Week 32 Frequency of clinically significant asthma exacerbations over 32 week treatment Ratio to baseline in blood eosinophils at Week 32
Other Objectives	Other Endpoints

 To determine the response to asthma clinical parameters 	
 Percentage of subjects achieving a 0.5-point or greater reduction from baseline in ACQ-5 score at Week 32 Percentage of subjects achieving a 4-point or greater reduction from baseline in SGRQ score at Week 32 Mean change from baseline in pre- and post bronchodilator FEV1 at Week 32 Frequency of exacerbations requiring ED visit/hospitalization during the treatment period Subject/Clinician rated response to therapy Mean change from baseline in treatment satisfaction questionnaire
Exploratory Objectives	Exploratory Endpoints

 To determine the effect on inflammatory biomarkers To characterize patient treatment benefit of mepolizumab 	
 Change from baseline in some inflammatory biomarkers expression at week 32 Subject Exit Interviews
Safety Objectives	Safety Endpoints

 To determine the safety, immunogenicity and tolerability of mepolizumab 	
 Incidence and frequency of Adverse/Serious Adverse Events (including systemic and injection site reactions) Clinically significant change in electrocardiogram (ECGs) Clinically significant change in vital signs

Objectives	Endpoints

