
 Adjusted means and the corresponding 95% confidence intervals will be presented by visit The estimated adjusted means will be presented using the observed marginal distributions of the sample covariates (OM option in LSMEANS statement). The Kenward and Roger method for approximating the denominator degrees of freedom and correcting for bias in the estimated variance-covariance of the fixed effects will be used (DDMF=KR). An unstructured covariance structure for the R matrix will be used by specifying 'type=UN' on the REPEATED line. Change from the baseline at each Visit X will be calculated by (Estimated Score at Visit X minus Estimated Score at Baseline) and the corresponding 95% confidence intervals. Adjusted means at each visit will also be presented. Plots of Least Squares (LS) mean change from baseline pre- and post bronchodilator FEV1 and 95% confidence intervals from the model will be generated at each visit.
On-treatment Phase
• See Primary Efficacy Statistical Analysis, Section 7.1.2

Other Statistical Analyses
Other Endpoint
• Subject rated response to therapy at Week 32
• Clinician rated response to therapy at Week 32
Results Presentation

 • The number and percentage of subjects in each response category will be presented for each visit. • The number of subjects with a missing responses at each visit will be presented in a separate category.
--

On-treatment Phase

 • An On-Treatment “de jure” analysis will also be performed which does not consider any data collected following treatment discontinuation (see On-Treatment definition within Section 10.4).

Other Statistical Analyses

Other Endpoint

 • Mean change from baseline in Treatment Satisfaction Questionnaire for Medication (TSQM-9)

Model Specification

 • The Mean Change at Week 32 will be tested to see if it is significantly different from zero using Wilcoxon signed-rank test

Model Checking & Diagnostics

 • Check for the extreme outliers by plotting the differences between TSQM-9 at Week 32 and Baseline

Model Results Presentation

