
 • Summary Statistics will be represented by study visit • The mean change at Week 32 will presented with the corresponding 95% CI and p-value in the table • The mean change at Week 32 will presented with the corresponding 95% CI in the figure
--

On-treatment Phase

 • An On-Treatment “de jure” analysis will also be performed which does not consider any data collected following treatment discontinuation (see On-Treatment definition within Section 10.4)
--

Other Statistical Analyses

Other Endpoint

 • Change from baseline in inflammatory biomarkers expression at week 32. The following biomarker parameters will be reported: CCL13, CCL17, ECP, EDN, Eotaxin1, Total IL-5, IL-13, MDC, Periostin, TSLP

Model Results Presentation

 • A log-transformation will be applied to each biomarker parameter prior to analysis. • Summary Statistics will be represented by study visit, including ratio to baseline • See Section 10.6.4 for further information regarding biomarker results below the lower limit of quantification

On-treatment Phase

 • An On-Treatment “de jure” analysis will also be performed which does not consider any data collected following treatment discontinuation (see On-Treatment definition within Section 10.4).

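### SAP 10.6.3: the TSQM-9 Overall Satisfaction formula can score as low as -8.3 (-12.5 with Item 7 or 8 missing), outside the SAP's own 0–100 limit

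*SAP*

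**What the plan says.** SAP 10.6.3 sets out TSQM-9 scoring. Scale scores run from 0 to 100, and "No computed score should be lower or higher than these limits". Protocol 7.3.2.1.4 gives the same range.

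Three scales are defined, each from three items:

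- Effectiveness (Items 1–3) and Convenience (Items 4–6): (sum − 3)/18 × 100, or (sum − 2)/12 × 100 with one item missing.
- Overall Satisfaction (Items 7–9): the rule begins "Overall Satisfaction scale: First recode Item 9", the recode being (Item 9 − 1) × 5/6. It then takes (sum − 3)/12 × 100. The alternative, introduced by "If any one Item is missing", is (sum − 2)/8 × 100.

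The item ranges are described only in Protocol 7.3.2.1.4: "Each of the 9 items is scored by the subject on a 5 or 7 point scale". The questionnaire itself is withheld from the public protocol.

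SAP 2.2 lists "Mean change from baseline in treatment satisfaction questionnaire" among the Other endpoints. SAP 8.1.2 states: "The Mean Change at Week 32 will be tested to see if it is significantly different from zero using Wilcoxon signed-rank test". It also plans a 95% confidence interval and p-value. The programming note to Table 2.36 asks for the three scales to be summarised separately.

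**The concern.** Subtracting 3 from a three-item sum brings the lowest score to 0 only if each item contributes at least 1. The recode has already brought Item 9 down to 0, so one unit is removed twice. A programmer who follows the SAP exactly can therefore produce a score that the same section forbids, and the SAP has no rule for handling it.

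The fault is not confined to the floor. A formula whose lowest point is wrong also places scores above 0 differently from a formula that fits the limits, and a range check would not reveal those. At stake is the numerical meaning of one TSQM-9 scale and of its change at Week 32.

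**Working it through.** **Inputs.** The limit, the recode and all formulas come from SAP 10.6.3. The two minima for Overall Satisfaction assume only that the lowest code of each item is 1. The other results also assume that Items 7 and 8 run 1–5 and Item 9 runs 1–7. That is inferred from the divisors (12 for three items, 8 for two, so 4 units per item) and from Item 9 alone being recoded.

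**Step 1: the scales that reproduce 0–100.** Effectiveness and Convenience, with items coded 1–7:

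- Complete: (3 − 3)/18 × 100 = 0 to (21 − 3)/18 × 100 = 100.
- One item missing: (2 − 2)/12 × 100 = 0 to (14 − 2)/12 × 100 = 100.

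**Step 2: Overall Satisfaction as printed.** Recoded Item 9 runs from (1 − 1) × 5/6 = 0 to (7 − 1) × 5/6 = 5.

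- Complete, lowest: (1 + 1 + 0 − 3)/12 × 100 = -8.3.
- Complete, highest: (5 + 5 + 5 − 3)/12 × 100 = 100.
- Item 7 or 8 missing, lowest: (1 + 0 − 2)/8 × 100 = -12.5; highest: (5 + 5 − 2)/8 × 100 = 100.
- Item 9 missing: (1 + 1 − 2)/8 × 100 = 0 to (5 + 5 − 2)/8 × 100 = 100.

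**Step 3: other readings.** None gives 0–100 for complete answers:

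| Reading | Range |
|---|---|
| Item 9 coded 1–5 | -8.3 to 86.1 |
| Items 7–9 all coded 1–7 | -8.3 to 133.3 |
| Items coded from 0 (Items 7–8: 0–4; Item 9: 0–6) | -31.9 to 76.4 |
| Recode read as Item 9 − (1 × 5/6) | -6.9 to 109.7 |

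**Step 4: how many patterns are negative.** There are 5 × 5 × 7 = 175 complete patterns. Two fall below 0. Items (7, 8, 9) = (1, 1, 1) gives -8.3, and (1, 1, 2) gives (1 + 1 + 0.833 − 3)/12 × 100 = -1.4.

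**Step 5: scores inside the limits.** Three repairs that each give exactly 0–100 for complete answers were compared with the printed formula over the 175 patterns. The difference is printed minus repaired.

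| Repair | Patterns that differ | Still different after truncating at 0 | Range of difference (points) |
|---|---|---|---|
| Recode Item 9 as 1 + (Item 9 − 1) × 4/6; keep (sum − 3)/12 | 150 | 149 | -8.3 to 0 |
| No recode; (sum − 3)/14 | 172 | 171 | -9.5 to +1.2 |
| Keep the printed recode; (sum − 2)/13 | 174 | 173 | -8.3 to 0 |

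Under the first repair the difference depends only on Item 9 and vanishes at its top category. Under each of the other two, 24 of the 25 patterns at Item 9's top category also differ. These are counts of possible response patterns, not of patients.

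**The case against.** The strongest reply is that the correct score cannot be known from these documents. The questionnaire is withheld, the scoring source is not available here, and the limit sentence may be meant as a check on the output. The practical reach is also small. TSQM-9 is an Other endpoint, only 2 of 175 patterns are negative, and the same formula applies at both visits. The -12.5 case needs a missing item, which should be rare because "the questionnaires must be reviewed by the investigator or designated study staff for completeness". SAP Table 5 and Table 2.36 show TSQM-9 as summaries only.

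Much of this stands, and it limits the size of the point. It does not remove the contradiction. The two minima need no knowledge of the source, only items coded from 1, the coding under which the SAP's other two scales fit 0–100. As an output check, the limit sentence gives no instruction for a score that fails it. A summary-only table would still show scores from the printed formula, and SAP 8.1.2 does plan a test: "The mean change at Week 32 will presented with the corresponding 95% CI and p-value in the table".

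Three stronger inferences are tempting and are not supported:

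- A fixed bias per category of Item 9. Against the 4/6 recode it would be (5/6 − 4/6)/12 × 100 = 1.39 points, with no error when Item 9 does not change. Both statements hold only against that recode, which the documents do not contain.
- That 150/175 = 86% of patients would be mis-scored. Pattern counts say nothing about how often patients give each answer.
- That the mean change leaves a 0–100 scale. A change in a 0–100 score can itself run from -100 to +100, so the limit applies to the scores and not to their change.

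**Conclusion.** The inconsistency is real. As printed, Overall Satisfaction can reach -8.3 with complete answers and -12.5 with Item 7 or 8 missing, against a stated floor of 0. No reading tested restores the range, and the SAP contains no truncation rule. On the inferred item ranges, complete scores span -8.3 to 100.

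Scores inside the limits are affected too: 150, 172 or 174 of 175 patterns differ from the printed formula, depending on the repair, and truncation at 0 corrects only one pattern in each case. The size, pattern and sometimes the sign of the difference depend on the repair, so no single shift in the mean change can be stated.

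Only the Overall Satisfaction scale and its Week 32 change are affected. Effectiveness, Convenience, and the primary and secondary endpoints are not, and no effect on the p-value is claimed. This is a minor correction.

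**What to change.** Before database freeze:

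1. Confirm which scoring source applies. The source that SAP 10.6.3 cites is listed in SAP section 9 under a title for TSQM version II, whereas Protocol 7.3.2.1.4 cites a validation of the TSQM-9 as well as the original TSQM validation.
2. Reconcile the Overall Satisfaction formula and its missing-item version with that source, so that both span exactly 0 to 100.
3. Do not use truncation at 0 in place of correcting the formula.

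As an illustration only, recoding Item 9 as 1 + (Item 9 − 1) × 4/6 gives 0 to 100 with both printed divisors, whichever item is missing. The source should decide the form.

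The cost is one SAP formula with its missing-item version, plus the matching programming. Data collection does not change.
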